### **2.2 Primary Objectives and Outcome Variables**

- Evaluate the safety and tolerability of GLS-1200 topical nasal spray
- Incidence of SARS-CoV-2 infection, confirmed by PCR relative to treatment group

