#### *Medical History*

Investigators should document all significant illnesses that the participant has experienced as Medical History in the last 6 months. Illnesses' first occurring or detected during the study and/or worsening of an existing illness that occurs after the first administration of study drug are documented as AEs on the electronic case report form (eCRF).

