# **7. EVALUATION OF SAFETY AND MANAGEMENT OF TOXICITY**

## **7.1 Safety Parameters**

### **7.1.1 Adverse Events (AEs)**

An adverse event (AE) is defined as any unfavorable and unintended change in the structure, function, or chemistry of the body, or worsening of a pre-existing condition, temporally associated with the use of a product whether or not considered related to the use of the product. In this study, such changes will be monitored, classified, and summarized, as Clinical or Laboratory AEs. Medical conditions/diseases present before starting the investigational drug will be considered adverse events only if they worsen after starting study treatment.

An unexpected AE is:

- Not identified in the Investigator's Brochure (IB) or otherwise not expected from the characteristics of the clinical material
- Not listed at the specificity or severity that has been previously observed

Study related AEs include the following:

- Pre- or post-treatment complications that occur as a result of protocol mandated procedure

- Any pre-existing condition that increases in severity, or changes in nature during or as a consequence of the study drug phase of a human clinical trial, will also be considered an AE
- Complications and termination of pregnancy; see Section 7.1.8 for additional information.
- All AEs that occur after enrollment and throughout the duration of the study will be recorded.

Study related AEs do not include the following:

- Elective medical or surgical procedures
- Non-elective medical or surgical procedures (e.g., surgery, endoscopy, tooth extraction, transfusion) performed; the condition that leads to the procedure is an AE
- Pre-existing diseases or conditions or laboratory abnormalities present or detected before study enrollment that do not worsen
- Situations where an untoward medical occurrence has not occurred (e.g., hospitalization for elective surgery, social and/or convenience admissions).
- Overdose without clinical sequelae
- Any medical condition or clinically significant laboratory abnormality with an onset date before the first dosing and not related to a protocol associated procedure is not an AE. It is considered to be pre-existing and will be documented on the medical history eCRF
- Any laboratory abnormality that is considered as non-significant or considered as related to another non-study related condition
- Uncomplicated pregnancy
- An induced elective abortion to terminate a pregnancy without medical reason

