### **8.3.1 Adverse events**

Treatment emergent AEs will be summarized by frequencies and will be presented by system organ class and preferred term with the number and percentage of participants affected. Frequencies will be presented with respect to maximum severity and to strongest relationship to Study Treatment. Multiple occurrences of the same AE will be counted only once following a worst-case approach with respect to severity and relationship to Study Treatment.

The proportion of participants experiencing any AEs (Grade 1-4) following treatment with study drug will be presented as part of the safety analysis set. The precision with which this sample result estimates the rate of similar AEs in the population represented by the study sample will be reported in terms of 95% confidence intervals (CI) around the sample proportions. This will provide 95% confidence that the rate of severe adverse effects is not greater than the upper limit of the CI around the proportion of participants with grade 3+ events in the study sample.

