## **9.1. Adverse Events**

An adverse event (AE) is defined as any unfavorable and unintended change in the structure, function, or chemistry of the body, or worsening of a pre-existing condition, temporally associated with the use of a product whether or not considered related to the use of the product. In this study, such changes will be monitored, classified, and summarized, as Clinical or Laboratory AEs. Medical conditions/diseases present before starting the investigational drug will be considered adverse events only if they worsen after starting study treatment. Verbatim terms on CRFs will be mapped to preferred terms (PTs) and system organ classes (SOCs) using the Medical Dictionary for Regulatory Activities (MedDRA) (version 23.0).

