### **9.1.4. Treatment-Emergent Adverse Events (TEAEs)**

#### **9.1.4.1. Definition of Treatment-Emergent**

TEAEs are events that either:

- a) began on or after the date and time of first dose or

b) had no recorded start date and the stop date is not before the date and time of first dose.

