### 9.1.5. Summaries of Adverse Events

An overall summary of AEs will display, by treatment, the number and percentage (with 95% exact binomial confidence interval) of subjects who had any TEAE, whose strongest TEAE relationship to study drug is related or not related, whose maximum TEAE severity is mild, moderate, or severe, who had any SAE, any Serious TEAE, any TEAE leading to study discontinuation, and any TEAE leading to death.

The following summaries (number and percentage of subjects) of AEs (by SOC and PT) will be provided by treatment:

- All TEAEs
- All TEAEs by strongest relationship
- All TEAEs by maximum severity grade
- All Serious AEs
- All Serious TEAEs
- All TEAEs leading to study discontinuation
- All TEAEs leading to death

These summaries will present the number and percentage of subjects with at least one qualifying AE. Subjects may have more than one AE per SOC and PT. Each summary will be ordered by descending order of incidence of SOC and PT within each SOC.

In addition to the by-treatment summaries, data listings will be provided for the following:

- All AEs (with a flag indicating whether the event is treatment emergent)
- SAEs
- AEs leading to study discontinuation
- Deaths

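### A new SARS-CoV-2 illness counts as a TEAE and no any-TEAE, severity or serious-TEAE row leaves it out, so prevented infections could mask spray-related events in those rows

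*SAP*

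**What the plan says.** Safety and infection are both primary. Protocol 2.2 lists "Evaluate the safety and tolerability of GLS-1200 topical nasal spray" beside the incidence of PCR-confirmed infection, and SAP 2.1 does the same.

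The AE definition is broad. SAP 9.1 states: "An adverse event (AE) is defined as any unfavorable and unintended change in the structure, function, or chemistry of the body", whether or not the product is thought to be the cause. Protocol 6.2.2 (Medical History) requires the following to be entered as AEs: "Illnesses' first occurring or detected during the study and/or worsening of an existing illness". Protocol 7.1.2 asks for the diagnosis to be entered in place of its signs and symptoms.

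The list in Protocol 7.1.1 of what is not a study AE does not name SARS-CoV-2 infection. Its nearest item is "Any laboratory abnormality that is considered as non-significant or considered as related to another non-study related condition".

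Under SAP 9.1.4.1 an event is treatment-emergent if it "began on or after the date and time of first dose". There is no end date and no exclusion of endpoint events.

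For reporting, Protocol 8.3.1 says: "The proportion of participants experiencing any AEs (Grade 1-4) following treatment with study drug will be presented as part of the safety analysis set", with 95% confidence intervals. SAP 9.1.5 and Table 14.3.1.1 give, by arm, "the number and percentage (with 95% exact binomial confidence interval) of subjects who had any TEAE". The same table has rows for related and not-related TEAEs, maximum severity, any SAE, any serious TEAE, TEAEs leading to discontinuation and TEAEs leading to death. None of the any-TEAE, severity or serious rows leaves infection out.

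**The concern.** One kind of event feeds both primary objectives in opposite directions. An infection prevented on GLS-1200 is a success for efficacy and also one participant fewer in the any-TEAE row. The design assumes 10% infection on placebo and 1% on GLS-1200. If the spray also causes local or systemic events, the two effects work against each other in that row, and the better the spray works, the smaller the visible excess. The severity and serious-event rows are affected in the same direction, but the documents give no figures from which to size them.

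The SOC/PT tables show infection as its own term. However, a participant can appear under several terms, so the proportion with any TEAE other than infection, and its interval, cannot be rebuilt from those tables. It would have to be derived after the fact from the listings.

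**Working it through.** **The plan's own figure.** SAP 4 and Protocol 8.7 give 80.8% power for 1% v 10%, 150 v 75 participants, alpha 0.05. Exact binomial enumeration of a two-sided pooled chi-square test with continuity correction gives 80.9%. The other five rows of Protocol Table 8.7-1 come out at 80.6% to 82.1%, against 80.0% to 80.4% stated. The design rates can therefore be used as they stand. They correspond to 0.01 × 150 = 1.5 expected infections on GLS-1200 and 0.10 × 75 = 7.5 on placebo.

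**Inputs.**
- Infection rates: p_G = 1% and p_P = 10% (SAP 4).
- b, the background rate of TEAEs other than infection. The documents give none, so 0% to 50% is assumed.
- e, the true excess of TEAEs caused by the spray. This is the unknown.
- f, the share of infections recorded as AEs. The documents do not settle it, so 100% and 50% are shown.
- Infection is assumed independent of other TEAEs.

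**Formula.**
- GLS-1200: P(any TEAE) = 1 − (1 − b − e)(1 − f·p_G)
- Placebo: P(any TEAE) = 1 − (1 − b)(1 − f·p_P)

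Setting the two equal gives the excess at which the row shows no difference: e* = (1 − b)[1 − (1 − f·p_P)/(1 − f·p_G)].

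**All infections recorded (f = 1).** 1 − 0.90/0.99 = 0.0909.

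| Background b | e* (points) |
|---|---|
| 0% | 9.1 |
| 20% | 7.3 |
| 40% | 5.5 |
| 50% | 4.5 |

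**Half recorded (f = 0.5).** 1 − 0.95/0.995 = 0.0452. So e* is 4.5, 3.6 and 2.7 points for b = 0, 20 and 40%.

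**Equal infection rates (10% v 10%).** e* = 0. The observed difference is 0.90·e, so the excess is diluted by a tenth and not masked.

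**Worked case, b = 20%, e = 9 points.**
- Infection left out: 29.0% v 20.0%, a difference of 9.0 points.
- Infection counted, f = 1: 1 − 0.71 × 0.99 = 29.7% v 1 − 0.80 × 0.90 = 28.0%, a difference of 1.7 points.
- Infection counted, f = 0.5: 1 − 0.71 × 0.995 = 29.4% v 1 − 0.80 × 0.95 = 24.0%, a difference of 5.4 points.
- Equal rates of 10%: 1 − 0.71 × 0.90 = 36.1% v 28.0%, a difference of 8.1 points.

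In whole participants, leaving infection out gives 44/150 (exact 95% interval 22.2% to 37.3%) v 15/75 (11.6% to 30.8%). Counting all infections gives 45/150 (22.8% to 38.0%) v 21/75 (18.2% to 39.6%). Nearly all of the change is on placebo.

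**Other rows of Table 8.7-1, b = 20%, f = 1.**

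| GLS-1200 v placebo infection | e* (points) |
|---|---|
| 0% v 7.3% | 5.8 |
| 2.5% v 13.5% | 9.0 |
| 5% v 18.1% | 11.0 |
| 7.5% v 22.1% | 12.6 |
| 10% v 25.7% | 14.0 |

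**The case against.** The case against is substantial, and much of it stands.

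- **Recording is inferred.** No section says that a positive study PCR is entered as an AE. Protocol 6.1.2 to 6.1.4 list adverse effects and any new SARS-CoV-2 diagnosis side by side, which can be read either way. The efficacy endpoint includes asymptomatic positives from scheduled swabs. Protocol 7.1.1 and 7.1.6 could keep these out of the AE data as laboratory findings without clinical significance. A reader might infer that the safety rows and the efficacy endpoint hold the same events; the documents support only an overlap of unknown size.
- **Some separation is already planned.** A reader might infer that no table separates infection at participant level. That is not so. Table 14.3.1.1 has a related-TEAE row with the same exact interval, and Tables 14.3.1.3 and 14.3.1.5 carry the split further. Each SOC row counts a participant once. If infections are judged unrelated, the related rows are largely free of the offset. The limit is that these rows rest on attribution, and SAP 9.1.2 counts possibly related and missing as related. Placebo is plain saline, so the taste of quinine could also influence attribution.
- **No formal comparison is planned.** Safety is reported with an interval within each arm, with no test or difference between arms. A reader might infer that harm is hidden in the GLS-1200 interval. It is not: counting infections can only raise that arm's rate and upper limit. What suffers is the side-by-side reading of the two arms.
- **All-cause counting is legitimate.** It follows the protocol's own AE definition and would show harm through more, or worse, infections. A reader might infer that tolerability should rest only on rows without infection. That would discard this information, and nothing in the documents calls for it.

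**Conclusion.** The point holds in a limited form. By the written definitions a new SARS-CoV-2 illness is a TEAE, and no any-TEAE, maximum-severity or serious-TEAE row is planned without it. At the design's infection rates the any-TEAE row could conceal a true spray excess of up to about 4.5 to 9.1 points if every infection is recorded (background 50% down to 0%). With half recorded the range is 2.7 to 4.5 points (background 40% down to 0%).

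These sizes rest on assumed background rates, on independence, and on the spray being as effective as the design supposes. With no efficacy there is dilution only. The related-TEAE and SOC/PT rows reduce the problem but do not supply an attribution-free row without infection. Sample size, power and the primary efficacy analysis are unaffected. This is a worthwhile, low-cost improvement to the safety reporting and does not invalidate it.

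**What to change.** 1. State in the SAP, consistently with Protocol 7.1.1 and 7.1.6, whether a PCR-confirmed infection is recorded as an AE, and whether this includes an asymptomatic positive. Otherwise the any-TEAE row may depend on site practice.
2. Keep every current all-cause row in SAP 9.1.5 and Table 14.3.1.1.
3. Add rows for any TEAE, each maximum-severity category and any serious TEAE, excluding confirmed SARS-CoV-2 infection, with the same exact 95% intervals. Define the exclusion by the infection preferred terms, plus a flag for AEs attributed to a PCR-confirmed infection, set blinded before database lock.
4. Say that tolerability will be judged from both sets together. The added rows show spray effects apart from infection, and the all-cause rows still show any harm through infection.

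The cost is SAP wording, a few table rows and one flag. No new data are needed. The flag involves judgement, because symptoms in the diary listing (Listing 16.2.6.2) such as runny nose, sneezing, sore throat or loss of smell could come from the spray or from infection. That is a further reason to keep both sets of rows.

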#### **7.1.4 Assessing Severity (Intensity)**

The Investigator will grade laboratory AEs and clinical AEs (based on discussions with study participants) using the NCI Common Terminology Criteria for Adverse Events v5.0:

- Mild (Grade 1)
- Moderate (Grade 2)
- Severe (Grade 3)
- Life-threatening consequences (Grade 4)
- Death related to AE (Grade 5)

Adverse events will be recorded on the eCRF at the severity reported by the investigator.

If an ongoing AE worsens or increases in its severity or its relationship to the study drug changes, a new AE entry for the event should be entered on the eCRF.

The following is a link to the grading scale:

[https://ctep.cancer.gov/protocolDevelopment/electronic\\_applications/docs/CTCAE\\_v5\\_Quick\\_Reference\\_5x7.pdf](https://ctep.cancer.gov/protocolDevelopment/electronic_applications/docs/CTCAE_v5_Quick_Reference_5x7.pdf)

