### **9.1.1. Severity**

AEs are graded by the investigator as Grade 1 (mild), Grade 2 (moderate), Grade 3 (severe), Grade 4 (potentially life threatening) or Grade 5 (death) according to the NCI Common Terminology Criteria for Adverse Events version 5.0.

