**Programming Note: Continue for each individual symptom.**

Table 14.2.3  
Cumulative Incidence of SARS-CoV-2 Seroconversion by Visit  
(ITT Population)

Visit Seroconverted	GLS-1200 (N=XX)	Placebo (N=XX)
Week 2		
n	x	x
Yes	x (xx.x%)	x (xx.x%)
No	x (xx.x%)	x (xx.x%)
Week 4		
n	x	x
Yes	x (xx.x%)	x (xx.x%)
No	x (xx.x%)	x (xx.x%)
Week 6		
n	x	x
Yes	x (xx.x%)	x (xx.x%)
No	x (xx.x%)	x (xx.x%)

The incidence of seroconversion is summarized based on results obtained at or prior to the visit.

Reference: Listing 16.2.6.3

Source: \\xx\xxx\xxx\xxx\xxxxx\xxxxxxxxxxxxx\xxxx\xxxx.sas      date      time

Table 14.3.1.1  
Overall Summary of Adverse Events  
(Safety Population)

	GLS-1200 (N=XX) n (%) [95% CI]	Placebo (N=XX) n (%) [95% CI]
Subjects with any TEAE	x (xx.x%) [xx.x% - xx.x%]	x (xx.x%) [xx.x% - xx.x%]
Subjects whose strongest TEAE relationship to study drug is related [1]	x (xx.x%) [xx.x% - xx.x%]	x (xx.x%) [xx.x% - xx.x%]
Subjects whose strongest TEAE relationship to study drug is not related [2]	x (xx.x%) [xx.x% - xx.x%]	x (xx.x%) [xx.x% - xx.x%]
Subjects whose maximum TEAE severity grade is Mild [3]	x (xx.x%) [xx.x% - xx.x%]	x (xx.x%) [xx.x% - xx.x%]
Subjects whose maximum TEAE severity grade is Moderate [3]	x (xx.x%) [xx.x% - xx.x%]	x (xx.x%) [xx.x% - xx.x%]
Subjects whose maximum TEAE severity grade is Severe [3]	x (xx.x%) [xx.x% - xx.x%]	x (xx.x%) [xx.x% - xx.x%]
Subjects with any SAE	x (xx.x%) [xx.x% - xx.x%]	x (xx.x%) [xx.x% - xx.x%]
Subjects with any serious TEAE	x (xx.x%) [xx.x% - xx.x%]	x (xx.x%) [xx.x% - xx.x%]
Subjects with any TEAE leading to study discontinuation	x (xx.x%) [xx.x% - xx.x%]	x (xx.x%) [xx.x% - xx.x%]
Subjects with any TEAE leading to death	x (xx.x%) [xx.x% - xx.x%]	x (xx.x%) [xx.x% - xx.x%]

AE = adverse event; SAE = Serious Adverse Event; TEAE = Treatment-Emergent Adverse Event; CI = Confidence Interval

The 95% CIs for the subject percentages are calculated using an exact binomial distribution.

[1] Related TEAEs are those with a relationship of related, possibly related, or probably related. If the relationship is missing, it is considered related.

[2] Not related TEAEs are those with a relationship of unlikely related or not related.

[3] Severity grades are determined according to the NCI Common Terminology Criteria for Adverse Events version 5.0.

Reference: Listing 16.2.7.1

Source: \\xx\\xxx\\xxx\\xxx\\xxxxxx\\xxxxxxxxxxxx\\xxxx\\xxxx.sas

date      time

Table 14.3.1.2  

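### Does the Severe row of the adverse-event summary miss the Grade 3-or-higher proportion that Protocol 8.3.1 bounds?

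*SAP*

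**What the plan says.** Protocol 7.1.4 grades events by CTCAE v5.0 and gives Grades 3, 4 and 5 separate labels, with severe belonging to Grade 3. SAP 9.1.1 does the same: "Grade 3 (severe), Grade 4 (potentially life threatening) or Grade 5 (death").

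Protocol 8.3.1 describes how precisely severe events will be estimated: "This will provide 95% confidence that the rate of severe adverse effects is not greater than the upper limit of the CI". The interval it means is the one "around the proportion of participants with grade 3+ events in the study sample".

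For the overall summary, SAP 9.1.5 asks for counts, percentages and exact binomial 95% intervals by treatment, including participants "whose maximum TEAE severity is mild, moderate, or severe". The shell for Table 14.3.1.1 has the same three severity rows. Their footnote reads "Severity grades are determined according to the NCI Common Terminology Criteria for Adverse Events version 5.0" and does not place Grades 4 and 5. The table also has rows, with intervals, for any TEAE, any SAE, any serious TEAE and any TEAE leading to death.

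For the tables by organ class and preferred term, SAP 9.1.5 lists "All TEAEs by maximum severity grade" without limiting the grades. The shell for Table 14.3.1.4, reused for 14.3.1.5, shows three columns and counts each participant once at the highest grade. SAP Appendix A allows the organisation of tables to change during programming.

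**The concern.** Safety and tolerability is a primary objective, and Table 14.3.1.1 is the only adverse-event table planned with confidence intervals. If the programmer applies the SAP 9.1.1 labels strictly, Severe means Grade 3 and nothing else. Two things follow. A participant whose worst event is life-threatening or fatal drops out of all three severity rows. And no planned row carries the Grade 3-or-higher proportion with the upper limit described in Protocol 8.3.1.

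The error would run in one direction only. A reader who took the Severe row as the protocol's bound would see a limit that is too low. In the extreme case the row could show zero participants although one had a Grade 4 event.

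**Working it through.** The documents state no adverse-event rate or limit, so there is no figure of the plan's own to reproduce. The check has three steps.

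**1. Do the passages contradict each other?** Let p3 be the rate of participants whose worst event is Grade 3, and p3+ the rate at Grade 3 or higher. Since p3 ≤ p3+, an upper limit U for p3+ is also an upper limit for p3. The sentence in Protocol 8.3.1 therefore holds whether severe means Grade 3 or higher (the natural reading) or Grade 3 only (the bound is then conservative). It sits alongside Protocol 7.1.4 and SAP 9.1.1 without conflict. What remains is that the SAP labels no row as Grade 3 or higher.

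**2. Can the quantity be obtained from planned output?** Each participant with a TEAE has one maximum grade. If every TEAE is graded:

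N(Grade 3 or higher) = N(any TEAE) − N(maximum mild) − N(maximum moderate)

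All three terms on the right are rows of Table 14.3.1.1, and the arm size is in the column header. The count and its exact interval follow. Under the strict reading the three severity rows would not add up to the any-TEAE row if a Grade 4-5 event occurred, so the omission would show in the table itself. Listing 16.2.7.1 gives the grade of every event.

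**3. How much could the label matter?** Inputs: planned arm sizes of 150 (GLS-1200) and 75 (placebo) from the Protocol synopsis and Table 8.7-1, taken as the Safety Population; the exact binomial method from SAP 9.1.5; and assumed event counts, because the documents give none. The upper limit for x participants out of n is the 0.975 quantile of a Beta(x+1, n−x) distribution. For x = 0 this reduces to 1 − 0.025^(1/n):

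- n = 150: 1 − 0.025^(1/150) = 2.43%
- n = 75: 1 − 0.025^(1/75) = 4.80%

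Assume one participant whose worst event is Grade 4 or 5, and 0, 1 or 2 whose worst event is Grade 3. The strict Severe row has x = 0, 1, 2; the Grade 3-or-higher count has x = 1, 2, 3.

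| Arm | At Grade 3 | Upper limit, Grade 3 only | Upper limit, Grade 3 or higher | Difference (points) |
|---|---|---|---|---|
| n=150 | 0 | 2.43% | 3.66% | 1.23 |
| n=150 | 1 | 3.66% | 4.73% | 1.07 |
| n=150 | 2 | 4.73% | 5.73% | 1.00 |
| n=75 | 0 | 4.80% | 7.21% | 2.41 |
| n=75 | 1 | 7.21% | 9.30% | 2.09 |
| n=75 | 2 | 9.30% | 11.25% | 1.95 |

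With no Grade 4-5 event, or if Severe is read as Grade 3 or higher, every difference is zero.

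**The case for a change.** The strongest case for acting is that the three-level wording is in the body of SAP 9.1.5, not only in a shell, so the Appendix A freedom over layout permits a repair but does not define the term. Two competent programmers could print different numbers for a summary that serves a primary objective. Serious is not the same as severe: a Grade 4 laboratory value need not be a serious event, so the serious and death rows do not add up to the missing category. The count can be recovered, but the interval the protocol describes is not itself a planned row. A one-line footnote would settle it.

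Most of that is accurate as description. The label is undefined, and the derivation does need complete grading. What does not stand is the consequence. An analyst who meets a Grade 4-5 event would pool it into the top category or add a column, since leaving a life-threatening event out of every severity row makes no sense and breaks the row total. Whether such an event occurred can be seen in pooled blinded data, so the choice need not wait for treatment codes. A Grade 4 event or death assessed as related also triggers a halt and investigation under Protocol 7.3.2, so it would be examined individually. Those rules work on counts and relatedness, not on this limit.

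**Conclusion.** The observation is textually correct, but it is a gap that analysts fill sensibly, and no change to the plan follows. The Protocol 8.3.1 bound is compatible with either meaning of severe. No event is lost, and the Grade 3-or-higher count follows from the same table by subtraction. No stated figure is wrong, and no test, stopping rule or conclusion depends on the limit.

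If the strict reading were programmed and one participant per arm had a Grade 4-5 maximum, the printed upper limit would be about 1.0 to 1.2 points low for GLS-1200 and 2.0 to 2.4 points low for placebo. These sizes rest on assumed counts of one Grade 4-5 participant and none to two at Grade 3, on the planned arm sizes as the Safety Population, and on complete grading. Without a Grade 4-5 event there is no effect.
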